10.3 Clinical laboratory evaluations

Laboratory data (chemistry, hematology and urinalysis) and changes from Baseline (if applicable) for numeric variables will be listed by treatment group and timepoint. Any laboratory measurements that are BLQ or ALQ will be handled as described in [Section 4.2.2](#). Values outside the reference range for the numeric variables will be flagged in the listings. The reference ranges will also be reported in the listings. In addition, the listings will include a flag for values identified as markedly abnormal MA as defined by the criteria outlined in [Section 13.2](#)**Error! Reference source not found..**

Chemistry and hematology parameters will be summarized by treatment group for both absolute values and changes from Baseline.

The laboratory variables to be included in the analysis are presented in [Table 10-1](#).

Table 10-1: Laboratory measurements

Category	Panel	Variable
Hematology	Red blood cell	RBC count, hemoglobin, hematocrit
	White blood cell	WBC count
	White blood cell differential	Absolute counts: ANC, basophils, eosinophils, ALC, monocytes Percentages: neutrophils/leukocytes, basophils/leukocytes, eosinophils/leukocytes, lymphocytes/leukocytes, monocytes/leukocytes

Table 10–1: Laboratory measurements

Category	Panel	Variable
	Platelet	Platelet count
Chemistry	Liver function	ALP, ALT, AST, GGT, total bilirubin ^a , LDH
	Enzymes	Creatine kinase, amylase
	Proteins	Total protein, albumin, alpha- and beta- globulins, hsCRP
	Kidney Function	Urea- nitrogen, creatinine
	Lipids	Triglycerides, total cholesterol, LDL cholesterol, HDL cholesterol,
	Electrolytes	Calcium, phosphate, sodium, potassium, chloride, and magnesium
	Hormones	Procalcitonin
Urinalysis ^b	Dipstick	pH, nitrite, protein, glucose, ketones, urobilinogen, bilirubin, blood,
	Urine Sediment	Leukocytes
	Quantitative	Albumin, creatinine, protein

ALC=absolute lymphocyte count; ALP=alkaline phosphatase; ALT=alanine aminotransferase; ANC=absolute neutrophil count; AST=aspartate aminotransferase; GGT=gamma-glutamyltransferase; HDL=high density lipoprotein; hsCRP=high sensitivity C-Reactive Protein; LDH=lactate dehydrogenase; LDL=low density lipoprotein; RBC=red blood cell; WBC=white blood cell

^a Direct bilirubin will also be measured when total bilirubin is elevated.

^b Urine microscopy will be performed if urine is positive for protein, blood, nitrite, or leukocytes.

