14.3 Planned safety analyses

14.3.1 Safety analyses

The incidence of study participants with TEAEs will be determined. Furthermore, the absolute and relative frequencies for study participants with a given TEAE with respect to the preferred term according to the latest available version of the Medical Dictionary for Regulatory Activities

(MedDRA®), will be determined within each system organ class. Additional tables will summarize TEAEs by maximum severity and causal relationship with rozanolixizumab, as judged by the investigator. Adverse events will be categorized by severity according to the National Institutes for Health CTCAE version 5.0 grading (National Institutes for Health, 2017). In case the CTCAE grading is not available, the intensity (mild/moderate/severe) will be utilized. The TEAEs leading to discontinuation of IMP and the serious TEAEs will also be summarized. The action taken, time of onset relative to dosing, actual dose received, and duration of each AE will be listed only.

For the continuous laboratory variables, the values and changes from Baseline will be descriptively summarized at each time point. For categorized values according to the reference range, shift tables from Baseline to each post-Baseline time point will be presented for selected variables to be defined in the SAP. Values outside the reference range will be flagged in the data listings.

Descriptive statistics will be presented for ECG value and changes from Baseline over time based on the mean of the triplicate assessments at each time point. Categorical analyses for QTc, eg, QTc increase >60msec, will also be performed.

Descriptive statistics will be reported for all vital sign measurements (including BP, PR, temperature, and body weight). Measured values and changes from Baseline will be summarized by time point.

Physical and neurological examination findings and the results of any pregnancy testing will be presented in listings only. Results will be listed for any study participants who complete a headache questionnaire, undergo stool sampling, or lumbar puncture, etc.

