2.2.1.2 Other safety variables

The other safety variables are:

- TEAEs leading to permanent withdrawal of investigational medicinal product (IMP)
- Vital sign values and changes from Baseline (systolic and diastolic blood pressure (BP), pulse rate (PR), body temperature, and body weight) at each scheduled assessment during Treatment and Observation Periods
- Physical examination findings
- Neurological examination findings
- 12-lead electrocardiogram (ECG) values and change from Baseline at each scheduled assessment during Treatment and Observation Periods
- Laboratory values and changes from Baseline at each scheduled assessment during Treatment and Observation Periods (hematology, clinical chemistry and urinalysis)
- Tuberculosis Signs and Symptoms Questionnaire at each scheduled assessment during Treatment and Observation Periods
- Values and change from Baseline in concentrations of total protein, albumin, α - and β -globulins at each scheduled assessment during Treatment and Observation Periods

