4.2.2 Safety Laboratory data

Measurements below the limit of quantification (BLQ) will be imputed with half of the lower limit of quantification (LLOQ) for the purpose of calculating change from Baseline and the respective descriptive statistics.

Measurements above the limit of quantification (ALQ), if applicable, will be imputed to the upper quantification limit for the calculation of changes from baseline and descriptive statistics. These rules will be applied to all safety laboratory data including clinical chemistry and urinalysis.

Descriptive statistics will be displayed if at most 33% of the individual data points at a timepoint are missing or are either not quantifiable (<LLOQ) or ALQ. Values that are BLQ will be replaced by the numerical value of the LLOQ/2 in this instance and values that are ALQ will be imputed to the value of the upper quantification limit. If more than 33% of the individual data points at a timepoint are missing or not quantifiable (BLQ and/or ALQ), no descriptive statistics will be presented.

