A listing will be presented by treatment group and study participant for all AEs. This will include the onset date/time and outcome date/time of the event (including relative days), the AE duration, days since first dose of IMP, days since most recent dose of IMP, actual dose received, study period, pattern of event, severity/intensity, relationship, action taken and outcome. In addition, the listing will flag AEs that led to discontinuation, TEAEs, serious adverse events (SAEs), AEs of interest, AEs of special interest and infusion reactions.

AEs of focus (ie, TEAEs that are a review focus for rozanolixizumab or the participant population) will be summarized, in separate tables, detailing all TEAEs meeting the following criteria described below:

- Headache using the UCB-defined search criteria.
- Gastrointestinal disturbances using the UCB-defined search criteria.
- Hypersensitivity reactions using the criteria SMQ='Hypersensitivity'

- Anaphylactic reactions using the criteria SMQ='Anaphylactic reaction' and the UCB-defined search criteria.
- Injection site reactions using the UCB-defined search criteria.
- Infusion reaction collected on the eCRF AE page.
- Opportunistic infections using the UCB-defined search criteria.
- Reductions in albumin and plasma proteins using the UCB-defined search criteria.
- Effects on the kidney using the criteria SMQ='Acute renal failure'
- Drug related hepatic disorders using the criteria SMQ='Drug related hepatic disorders - comprehensive search'.

For each of the above mentioned AEs of focus the following summaries will be presented:

- Incidence of all AEoFs by SOC, HLT and PT
- Incidence of all AEoFs by Relationship, SOC, HLT and PT
- Incidence of all serious AEoFs by SOC, HLT and PT
- Incidence of all AEoFs by Maximum Intensity, SOC, HLT and PT

UCB definitions for AEoF are found in a separate document "Adverse Events (AEs) of Focus for the rozanolixizumab Program" version 1.3, dated 04 Aug 2020.

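### SAP 10.3 specifies no summary table for urinalysis, although the protocol and other SAP sections call for one and the change is not declared

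*SAP*

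**What the plan says.** The protocol commits to summaries without excluding urine. Section 14.3.1 reads: "For the continuous laboratory variables, the values and changes from Baseline will be descriptively summarized at each time point". It adds shift tables for laboratory variables that the SAP is to select.

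The SAP repeats the safety variable in 2.2.1.2: "Laboratory values and changes from Baseline at each scheduled assessment during Treatment and Observation Periods (hematology, clinical chemistry and urinalysis". Section 4.2.2 sets rules for non-quantifiable values in descriptive statistics and then states their reach: "These rules will be applied to all safety laboratory data including clinical chemistry and urinalysis".

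Section 10.3 handles listings and tables differently. For listings: "Laboratory data (chemistry, hematology and urinalysis) and changes from Baseline (if applicable) for numeric variables will be listed by treatment group and timepoint". For summaries: "Chemistry and hematology parameters will be summarized by treatment group for both absolute values and changes from Baseline". The sentence that follows introduces Table 10-1 with "The laboratory variables to be included in the analysis are presented in", and the quantitative urinalysis row of that table reads "Albumin, creatinine, protein".

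Among the adverse events of focus, SAP 10.2 includes "Effects on the kidney using the criteria SMQ='Acute renal failure".

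**The concern.** A programmer building tables from SAP 10.3 would produce them for chemistry and hematology and none for urine. That drops a summary the protocol promises for a declared safety variable, in a study whose primary objective is long-term safety, and SAP 3.9 does not record it as a change.

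Kidney effects are a declared review focus, but the focus table is driven by a search of reported adverse event terms. A slow drift in urinary albumin or protein that nobody reports as an event would be seen only by reading individual listings. A listing gives no incidence, time trend or comparison of the newly treated and previously treated groups. Reductions in albumin and plasma proteins are a separate adverse event of focus, and urinary albumin and protein would help to interpret them.

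**Working it through.** The main check is a comparison of passages; the plan states no figure to reproduce.

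**What each passage requires for urinalysis**

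| Place | Listing | Summary statistics |
|---|---|---|
| Protocol 14.3.1 | All documented data are listed (14.2) | Yes, for continuous laboratory variables |
| SAP 2.2.1.2 | – | Values and changes from Baseline are a safety variable |
| SAP 3.1 | Yes | General rule for continuous variables, by group and visit |
| SAP 4.2.2 | – | Presupposed: imputation and suppression rules cover urinalysis |
| SAP Table 10-1 | – | Urine albumin, creatinine and protein named for analysis |
| SAP 10.3, summary sentence | – | Chemistry and hematology only |
| SAP 3.9 | – | No change declared |
| SAP Table 13-2 | Markedly abnormal flag | Serum creatinine and eGFR have criteria; no urine variable does |

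Everything above the 10.3 row points to a urinalysis summary. The one sentence that specifies the laboratory tables leaves it out, and 3.9 is silent. No laboratory shift table is selected either, although Protocol 14.3.1 left that choice to the SAP.

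**What remains covered.** SAP Table 10-1 places urea-nitrogen and creatinine under chemistry, so both are summarised, as are serum albumin and total protein. SAP 10.2 tabulates all treatment-emergent adverse events by system organ class, high level term and preferred term. The 10.3 listing prints reference ranges and flags numeric values outside them.

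**How many samples are involved.** The protocol gives two answers, both counted after Screening.

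- Table 5-1, combined laboratory row: Visits 2, 3, 4, 5 and 8 (5) + Visits 10, 14, 18 and 22 (4) + Visits 12, 16, 20 and 24 (4) = 13 in Part 1. Part 2 site visits: 52 / 4 = 13. Visits 26 and 29: 2. Total 13 + 13 + 2 = 28 at most.
- Section 8 visit lists: the same 13 plus Visit 6 = 14 in Part 1. Part 2 site visits (8.3.1): hematology, clinical chemistry and a urine pregnancy test, with no urinalysis sample, so 0. Visits 26 and 29: 2. Total 14 + 0 + 2 = 16.

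The difference is 28 − 16 = 12: thirteen fewer in Part 2 and one more at Visit 6. The finding does not depend on which count is right.

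**Why a ratio would help.** Let a sample have albumin *a* and creatinine *c*. Assume, purely as an illustration, that the next sample is three times as concentrated with no change in kidney leakage. Albumin becomes 3*a*, a threefold rise, while the ratio is 3*a* / 3*c* = *a* / *c*, unchanged. Neither document derives such a ratio, although the SAP lists all the components.

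**The case against.** The strongest reply is that the SAP can be read as including urinalysis. Section 1 defaults to the protocol unless the SAP specifies otherwise, 3.1 summarises continuous variables as a general rule, Table 10-1 lists the urine variables for analysis, and 4.2.2 covers them. Section 10.3 never says that urinalysis will not be summarised. This rules out saying that the data will never be tabulated. It does not remove the problem: the default yields where the SAP is specific, 10.3 is specific about what is summarised, and none of the other provisions sets up a urinalysis table.

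A reader might infer more than the documents support.

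- *Kidney safety is not tabulated.* It is, through serum chemistry and adverse event tables. An abnormal laboratory finding can itself be an adverse event under Protocol 9.1.1.1. The gap is confined to urinary measures.
- *Abnormal urine results go unflagged.* Reference-range flags apply to numeric urine values in the listings. Only the markedly abnormal flag has no urine criterion.
- *Leaving out the ratio, or a dipstick shift table, breaches the protocol.* The protocol promises no ratio and leaves the choice of shift-table variables to the SAP.
- *Up to 28 samples per participant go unsummarised over 76 weeks.* Thirteen of those rest on a combined row label in Table 5-1 that the Part 2 visit list does not support.

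**Conclusion.** The point holds as an internal contradiction and an undeclared departure from Protocol 14.3.1: no urinalysis summary table is specified, and urine values are listed only. It concerns the three quantitative analytes in SAP Table 10-1. Of these, Protocol Table 9-5 names albumin and creatinine outside the dipstick group, while protein appears once, among the dipstick-type items.

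The primary safety variable, the occurrence of treatment-emergent adverse events, is unaffected. In a descriptive extension study this is a reporting gap that should be closed before database lock, and it carries more weight than missing detail because kidney effects are a declared focus. It concerns reporting only and touches no clinical rule.

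The conclusion assumes that 10.3 is followed as written. The volume of urine data, 16 or up to 28 samples per participant after Screening, stays open until the protocol is reconciled.

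**What to change.** Replace the summary sentence in SAP 10.3 with: *Absolute values and changes from Baseline will be tabulated by treatment group and timepoint for chemistry, hematology and the quantitative urinalysis variables.* If listing-only is intended, say so in 3.9 and give the reason.

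As an improvement, derive urine albumin/creatinine and protein/creatinine ratios from the same sample and state their units. Set a numerator below the limit of quantification to LLOQ/2, as in 4.2.2. Summarise the ratios by median and range, with percentage change from Baseline. A shift table from Baseline for dipstick protein and blood is optional.

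Reconcile Table 5-1 with Sections 8.2.5 and 8.3.1 on urinalysis at Visit 6 and at Part 2 site visits.

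The SAP change needs wording and a few extra tables, with no new data collection. Some tables may come out empty, because 4.2.2 suppresses statistics when more than 33% of values at a timepoint are missing or not quantifiable.

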10.3.1 Potential drug-induced liver injury

A separate table will present study participants who meet one or more of the following potential drug-induced liver injury (PDILI) criteria at any visit:

- Aspartate aminotransferase (AST): >3 x ULN, >5 x ULN, >8 x ULN, >10 x ULN, >20 x ULN
- Alanine aminotransferase (ALT): >3 x ULN, >5 x ULN, >8 x ULN, >10 x ULN, >20 x ULN
- AST or ALT: >3 x ULN, >5 x ULN, >8 x ULN, >10 x ULN, >20 x ULN
- Total bilirubin (TBL): >1.5 x ULN, >2 x ULN
- Alkaline phosphatase (ALP) >1.5 x ULN
- AST or ALT >3 x ULN, with TBL >1.5 x ULN
- AST or ALT >3 x ULN, with TBL >2 x ULN
- (ALT or AST increase >3 x ULN) and Total bilirubin >2 x ULN and ALP <2 x ULN (Hy's Law)

- Incidence of potential hepatotoxicity with symptoms potentially associated with hepatitis or hypersensitivity (participants meeting laboratory criteria for pDILI for at least 1 visit and reporting at least 1 symptom potentially associated with hepatitis or hypersensitivity according to the Investigator on the pDILI CRF.)
- Incidence of potential hepatotoxicity with no symptoms potentially associated with hepatitis or hypersensitivity (participants meeting laboratory criteria for pDILI for at least 1 visit and not reporting any symptom potentially related to hepatitis or hypersensitivity according to the Investigator pDILI CRF.)

The laboratory results listing will flag study participants who are experiencing PDILI including Hy's Law.

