6.4.2 Potential drug-induced liver injury IMP discontinuation criteria

Study participants with potential drug-induced liver injury (PDILI) must be assessed to determine if IMP must be discontinued. In addition, all concomitant medications and herbal supplements that are not medically necessary should also be discontinued.

The PDILI criteria below require **immediate and permanent** discontinuation of IMP:

- Study participants with either of the following:
 - ALT or AST $\geq 5\text{xULN}$
 - ALT or AST $\geq 3\text{xULN}$ and coexisting total bilirubin $\geq 2\text{xULN}$

The PDILI criterion below requires immediate discontinuation of IMP:

- Study participants with ALT or AST $\geq 3\text{xULN}$ who exhibit temporally associated symptoms of hepatitis or hypersensitivity. Hepatitis symptoms include fatigue, nausea, vomiting, right upper quadrant pain or tenderness. Hypersensitivity symptoms include fever (without clear alternative cause), rash, or eosinophilia (ie, $>5\%$).

If a nondrug-related cause for the symptoms can be confirmed, these study participants may resume IMP administration after discussion with the responsible UCB physician, but only when the requirements for rechallenge with IMP as provided in Section 9.2.1.2.1 are followed.

The PDILI criterion below allows for study participants to continue on IMP at the discretion of the investigator.

- Study participants with ALT or AST $\geq 3 \times$ ULN (and $\geq 2 \times$ Baseline) and $< 5 \times$ ULN, total bilirubin $< 2 \times$ ULN, and no eosinophilia (ie, $\leq 5\%$), with no fever, rash, or symptoms of hepatitis (eg, fatigue, nausea, vomiting, right upper quadrant pain or tenderness).

Evaluation of PDILI must be initiated as described in Section 9.2.1. If study participants are unable to comply with the applicable monitoring schedule, IMP must be discontinued immediately.

Investigators should attempt to obtain information on study participants in the case of IMP discontinuation to complete the final evaluation. Study participants with PDILI should not be withdrawn from the study until investigation and monitoring are complete. All results of these evaluations and observations, as well as the reason(s) for IMP discontinuation and study participant withdrawal (if applicable), must be recorded in the source documents. The eCRF must document the primary reason for IMP discontinuation.

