9.1.1.3 Adverse events of special interest

An AE of special interest is any AE that a regulatory authority has mandated be reported on an expedited basis, regardless of the seriousness, expectedness, or relatedness of the AE to the administration of a UCB product/compound.

Potential Hy's Law, defined as $\geq 3 \times \text{ULN}$ ALT or AST with coexisting $\geq 2 \times \text{ULN}$ total bilirubin in the absence of $\geq 2 \times \text{ULN}$ ALP, with no alternative explanation for the biochemical abnormality, must ALWAYS be reported to UCB as an AE of special interest (ie, without waiting for any additional etiologic investigations to have been concluded). Follow-up information should then be reported if an alternative etiology is identified during investigation and monitoring of the study participant.

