3.9 Changes to protocol-defined analyses

- CIDP relapse (maximum grip strength as assessed by site personnel) is defined as a clinically important deterioration from Baseline in grip strength as measured by site personnel, ie, a decline of $>14\text{kPa}$. Additionally, relapses defined by decline of $>8\text{kPa}$ will be investigated.
- The FAS definition is clarified to include at least one valid post baseline iRODS assessment result.
- The PD-PPS will be handled as a subset of the SS instead of the FAS as defined in the protocol to not exclude data due to missing efficacy results.
- To prevent bias in efficacy evaluation, an efficacy assessment is considered invalid, if that assessment follows the first intake of rescue medication. Assessments on the same day as first intake of rescue medication are considered valid.
- The MFAS is included as an additional analysis set in the SAP and was not part of the final clinical study protocol (CSP). This was added as a sensitivity analysis, to ensure the robustness of the efficacy results in relation to dose variation.
- Elevated liver function tests and potential drug induced liver injury criteria are harmonized across the rozanolixizumab program. Protocol-defined criteria are updated to match UCB's standard evaluations. Please refer to Section 10.3.1 for a list of the criteria that will be evaluated.

$\geq 3\times\text{ULN}$ ALT or AST with coexisting $\geq 2\times\text{ULN}$ total bilirubin in the absence of $\geq 2\times\text{ULN}$ ALP

will instead be defined as

(ALT or AST increase $\geq 3\times\text{ULN}$) and Total bilirubin $\geq 2\times\text{ULN}$ and ALP $<2\times\text{ULN}$ to match program standards and general medical definitions.

- The study variable “Change in CIDP-specific auto-antibody levels in serum from Baseline during Treatment and Observation Periods” will not be analyzed in scope of this SAP.

Sampling dates are captured in the CRF and will be listed. The samples’ results will not be part of this study’s database and instead analyzed and reported separately. The same is true for exploratory biomarkers RNA, proteins and metabolites variables.

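### The Hy's Law row in SAP 10.3.1 uses >3 and >2 x ULN where SAP 3.9 and the protocol use ≥3 and ≥2 x ULN, so results exactly on a cut-off drop out of that row

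*SAP*

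**What the plan says.** **Protocol.** Section 9.1.1.3 describes potential Hy's Law as ALT or AST ≥3 x ULN together with total bilirubin ≥2 x ULN, without ALP ≥2 x ULN and with no other explanation. Such a case "must ALWAYS be reported to UCB as an AE of special interest". Section 6.4.2 uses inclusive cut-offs too. Permanent discontinuation of IMP applies at ALT or AST ≥5 x ULN, or at ≥3 x ULN with bilirubin ≥2 x ULN. Immediate discontinuation applies at ≥3 x ULN with symptoms of hepatitis or hypersensitivity.

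**SAP 3.9.** The liver criteria are said to be harmonised across the rozanolixizumab programme, with the list given in 10.3.1. For Hy's Law alone, 3.9 writes out the definition that is to apply: ALT or AST ≥3 x ULN, bilirubin ≥2 x ULN and ALP <2 x ULN. The stated reason is "to match program standards and general medical definitions".

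**SAP 10.3.1.** The row that carries the Hy's Law label is "ALT or AST increase >3 x ULN) and Total bilirubin >2 x ULN and ALP <2 x ULN". The single-parameter rows are strict as well: "AST or ALT: >3 x ULN, >5 x ULN, >8 x ULN, >10 x ULN, >20 x ULN" and "Total bilirubin (TBL): >1.5 x ULN, >2 x ULN". There are also rows for AST or ALT >3 x ULN combined with bilirubin >1.5 x ULN and with bilirubin >2 x ULN. The symptom row counts "participants meeting laboratory criteria for pDILI for at least 1 visit and reporting at least 1 symptom" on the investigator's form.

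**The concern.** A programmer cannot follow both 3.9 and 10.3.1. The table will be built from 10.3.1, which is the version that departs from the protocol. Long-term safety is the primary objective, and the Hy's Law count is one of the liver results a reader looks for first. A case at the boundary could be reported as an adverse event of special interest and lead to permanent discontinuation under the protocol, while the Hy's Law row shows zero. The laboratory listing is also to flag PDILI, including Hy's Law. If that flag is programmed from the 10.3.1 rows, it has the same gap.

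**Working it through.** There is no plan figure to reproduce. The check applies the written rules to the same laboratory values. Let T = ALT or AST, B = total bilirubin and P = ALP, each as a multiple of ULN.

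**Rules**
- Hy's Law, SAP 3.9 (same laboratory thresholds as Protocol 9.1.1.3): T ≥ 3, B ≥ 2, P < 2.
- Hy's Law row, SAP 10.3.1: T > 3, B > 2, P < 2.
- IMP discontinuation, Protocol 6.4.2: T ≥ 5; or T ≥ 3 with B ≥ 2; or T ≥ 3 with symptoms.
- Other numeric rows of 10.3.1: T > 3, 5, 8, 10, 20; B > 1.5, 2; P > 1.5; T > 3 with B > 1.5; T > 3 with B > 2.

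**Cases at and near the cut-offs**

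| T, B, P | Protocol | Hy's Law in 3.9 | Hy's Law row in 10.3.1 | Numeric rows of 10.3.1 entered |
|---|---|---|---|---|
| 3.0, 2.0, 1.0 | permanent stop; special interest if no other explanation | yes | no | B > 1.5 |
| 3.0, 2.5, 1.0 | same | yes | no | B > 1.5, B > 2 |
| 4.0, 2.0, 1.0 | same | yes | no | T > 3; B > 1.5; T > 3 with B > 1.5 |
| 3.01, 2.01, 1.0 | same | yes | yes | T > 3; B > 1.5; B > 2; both combined rows; Hy's Law |
| 5.0, 1.0, 1.0 | permanent stop | no | no | T > 3, not T > 5 |
| 3.0, 1.0, 1.0 with symptoms | immediate stop | no | no | none |

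**Grid check.** Steps of 0.1 x ULN were used, with T from 0 to 10, B from 0 to 4, P from 0 to 3, and symptoms yes or no.

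*Hy's Law under 3.9 but not in the 10.3.1 row.* These are exactly the points with T = 3.0 or B = 2.0.
- T = 3.0 with B from 2.0 to 4.0 gives 21 pairs.
- B = 2.0 with T from 3.0 to 10.0 gives 71 pairs.
- One pair is shared, so 21 + 71 − 1 = 91.
- With 20 values of P below 2 and two symptom states, 91 × 20 × 2 = 3,640 points.
- None is absent from the whole table, because B ≥ 2 always satisfies B > 1.5.

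*Discontinued under the protocol and in no numeric row.* This occurs only at T = 3.0 with symptoms and with B and P both ≤ 1.5, which gives 16 × 16 = 256 points. None of these is a Hy's Law case.

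The counts show where the rules disagree. They are not probabilities.

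**After the change.** With ≥3 and ≥2 in the Hy's Law row, it agrees with 3.9 at every grid point.

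**How a boundary value can arise.** As an illustration with an assumed ULN of 40 U/L, a result of 120 U/L gives 120 / 40 = 3.0 exactly.

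**The case against.** Four points can be made on the other side.

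**The remaining rows are a disclosed change.** Section 3.9 says the protocol criteria are updated to the sponsor's standard and refers to 10.3.1 for them. A reader might infer that the SAP contradicts itself throughout 10.3.1. It does not: 3.9 spells out an inequality for Hy's Law only. This stands, and it limits the internal contradiction to that definition. Section 3.9 does not say, however, that inclusive cut-offs have become strict.

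**The case is visible elsewhere.** PDILI events must be reported as adverse events (Protocol 9.2.1). SAP 10.2 tabulates events of special interest, discontinuations due to adverse events and drug-related hepatic disorders. The event of special interest also requires that there be no other explanation, which the laboratory row does not test, so the two counts need not agree even with identical thresholds. This stands and keeps the point small.

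**The slip may be in 3.9.** The replacement definition there is logically the same as the protocol text it replaces, since the absence of ALP ≥2 x ULN is ALP <2 x ULN. A declared change that changes nothing could mean the strict version was intended. The documents cannot settle intent. But 3.9 is where the SAP declares the definition, and it agrees with the protocol. If the strict version is wanted, 3.9 is wrong and has to say so. Either way one section must change.

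**Making every row inclusive would cause new conflicts.** SAP Table 13-2 sets marked abnormality for AST and ALT at >5.0 x ULN. The protocol is mixed at 8x (≥8 x ULN for the hepatology consultation in Table 9-6, ALT >8 x ULN in a Table 9-7 footnote). No protocol PDILI criterion uses 10x or 20x. This stands, and a blanket replacement is not recommended.

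**Conclusion.** The SAP holds two Hy's Law definitions, and the one used for the table leaves out cases at exactly 3.0 x ULN ALT or AST, or exactly 2.0 x ULN bilirubin, that meet 3.9 and the protocol's laboratory thresholds. This is a minor point, worth correcting because the statement affected is a key safety one and the correction is nearly free.

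Two stronger readings are not supported.
- A reader might infer that a Hy's Law participant can vanish from the liver table. Each such case still enters at least the bilirubin >1.5 x ULN row, and a case at 5.0 x ULN still enters the >3 x ULN row. Absence from every numeric row requires exactly 3.0 x ULN with symptoms and with bilirubin and ALP both ≤1.5 x ULN. Whether that participant also misses the symptom row depends on whether its laboratory criteria mean the listed rows, which 10.3.1 does not say.
- A reader might infer that a stopping or reporting threshold is altered. Section 10.3.1 defines a descriptive table; discontinuation and reporting follow the protocol.

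The conclusion assumes that rows are programmed as written and that reportable events are recorded as the protocol requires.

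**What to change.** 1. In SAP 10.3.1, write the Hy's Law row as ALT or AST ≥3 x ULN, total bilirubin ≥2 x ULN and ALP <2 x ULN, matching SAP 3.9 and Protocol 9.1.1.3.
2. Write the parallel row for AST or ALT with bilirubin at 2 x ULN using ≥3 and ≥2, matching Protocol 6.4.2.
3. For the single-parameter 3x and 5x transaminase rows, either add the protocol's inclusive cut-off or state in 3.9 that the strict inequality is a deliberate departure. At 5x, keep the choice consistent with SAP Table 13-2. The same sentence in 3.9 can cover the single bilirubin 2x row, so that a result of exactly 2.0 x ULN that enters a combined row but not that one is explained.
4. Leave the 8x, 10x and 20x rows unchanged.

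The cost is a wording edit to the SAP and a matching check of the table and listing-flag programs. No new data are needed, and the protocol's discontinuation and reporting rules are untouched.
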